6.1 Screening

Written informed consent will be obtained by the Investigator as specified in Section 11.3 prior to any study related procedures being performed. Obtaining the informed consent can be performed on a separate visit prior to the screening period. Screening procedures may be performed over more than one day.

Patients will be screened to determine eligibility against the inclusion and exclusion criteria between 7 and 21 days before the first dose of study treatment. There are no fasting requirements for the screening visit. Patients must withhold long acting bronchodilators, ipratropium and salbutamol (or Combivent[®]) prior to screening as defined in Section 5.9.1.

The following assessments will be performed:

- Recording of demographic information, including height and weight
- Recording of medical/surgical and disease history
- Recording of prior medications and therapies
- Vital signs
- Full physical examination
- Alcohol breath test
- 12-lead ECG
- Chest X-ray (unless historical X-ray performed in last 12 months is available)
- Whole body plethysmography training and assessment of capacity to perform procedure (may be performed more than once as required)
- Pre-salbutamol spirometry
- Reversibility test (4 puffs salbutamol)
- Post-salbutamol spirometry (starting 20 to 30 minutes after administration)
- Place 24 hour Holter monitor; patients will be instructed to return the next day for removal of the Holter monitoring
- Blood and urine samples for laboratory safety tests (haematology, biochemistry, urinalysis), pregnancy tests (female patients of childbearing potential only), and viral serology. The urine pregnancy test result should be obtained prior to chest X-ray for females of childbearing potential.
- Instruct patients to stop all long acting bronchodilators for the duration of the study
- Inhalation training for use of nebuliser and DPI. This will be verbal instruction and demonstration of the device
- Questioning for adverse events

If the patient meets the inclusion and none of the exclusion criteria they will be instructed to return in 7 to 21 days for Treatment Period 1, Day 1.

6.2 Treatment Period 1; Day 1

This visit is approximately 72 hours in duration. Patients must withhold long acting bronchodilators, ipratropium and salbutamol (or Combivent[®]) prior to the start of the treatment period as defined in Section 5.9.1. Patients will be fasting from 2 hours pre-dose until 2 hours post-dose (except for water) and other restrictions defined in Section 5.4.2 should be adhered to.

At the start of Treatment Period 1, patients will be evaluated to ascertain if the inclusion and exclusion criteria are still met. If so, patients will receive a randomisation number. The following assessments will be performed:

6.2.1 **Pre-Dose Assessments**

- Confirm that respiratory medications were withheld as required. If not reschedule the visit for within the permitted windows
- Questioning for adverse events
- Urine pregnancy test (females of childbearing potential only)
- 12-lead ECG
- Vital signs
- Brief physical examination
- Spirometry
- Whole body plethysmography
- Inhalation training for use of nebuliser and DPI. This will be verbal instruction and demonstration of the device

6.2.2 Study Treatment Administration

Patients will be dosed with open label tiotropium DPI 18 mcg (two inhalations from one capsule) followed immediately (within 2 minutes) with either blinded RPL554 or placebo using a nebuliser according to randomisation scheme. At 12 hours (± 30 minutes) after the morning dose, the second dose of RPL554 or placebo will be administered by nebulisation.

6.2.3 **Post-Dose Assessments (after morning doses only)**

- Spirometry at 5, 15 and 30 minutes and 1, 1.5, 2, 4, 6, 8 and 12 hours
- Vital signs at 30 minutes and 1, 2, 4, 6, 8 and 12 hours
- 12-lead ECGs at 2 and 4 hours
- Questioning for adverse events

Patients will stay at the study centre overnight, unless they need to return home overnight and this is agreeable to the Investigator.

6.3 Treatment Period 1; Day 2

Patients will be fasting from 2 hours pre-dose until 2 hours post-dose (except for water) and other restrictions defined in Section 5.4.2 should be adhered to. The following assessments will be performed:

6.3.1 **Pre-Dose Assessments**

- Questioning for adverse events
- Place 24 hour Holter monitor (at least 30 minutes pre-dose)
- 12-lead ECG
- Vital signs
- Spirometry
- Whole body plethysmography

6.3.2 Study Treatment Administration

Patients will be dosed with open label tiotropium DPI 18 mcg (two inhalations from one capsule) followed immediately (within 2 minutes) with either blinded RPL554 or placebo using a nebuliser according to randomisation scheme. At 12 hours (± 30 minutes) after the morning dose, the second dose of RPL554 or placebo will be administered by nebulisation.

6.3.3 **Post-Dose Assessments (after morning doses only)**

- 12-lead ECGs at 2 hours
- Vital signs at 30 minutes and 1, 2, 3, 4 and 12 hours
- Spirometry at 15 and 30 minutes and 1, 2, 3 and 4 hours
- Whole body plethysmography at 1.25 hours
- Questioning for adverse events
- Continue 24 hour Holter monitoring to at least 24 hours post-dose and prior to Day 3 dose

Patients will stay at the study centre overnight, unless they need to return home overnight and this is agreeable to the Investigator.

6.4 Treatment Period 1; Days 3 to 4

Patients must remain in the unit for at least 24 hours after morning dosing on Day 3. Patients will be fasting from 2 hours pre-dose until 2 hours post-dose (except for water) and other restrictions defined in Section 5.4.2 should be adhered to. The following assessments will be performed:

6.4.1 **Pre-Dose Assessments**

- Questioning for adverse events
- 12-lead ECG
- Vital signs
- Spirometry
- 24 hour Holter monitor removed
- Blood sample for pharmacokinetics

6.4.2 Study Treatment Administration

Patients will be dosed with open label tiotropium DPI 18 mcg (two inhalations from one capsule) followed immediately (within 2 minutes) with either blinded RPL554 or placebo using a nebuliser according to randomisation scheme. There is no evening dose of study treatment on Day 3 of each period.

6.4.3 **Post-Dose Assessments**

Note: 24 hour assessments will be performed in the morning on Day 4 prior to discharge from the study centre.

- 12-lead ECGs at 2, 4 and 24 hours
- Vital signs at 30 minutes and 1, 2, 4, 6, 8 and 24 hours
- Spirometry at 5, 15 and 30 minutes and 1, 1.5, 2, 4, 6, 8, 12, 15 and 24 hours
- Questioning for adverse events

- Blood samples for pharmacokinetics at 5, 30 and 45 minutes and 1, 1.5, 2, 4, 8, 12, 15 and 24 hours
- Blood sample for laboratory safety tests (haematology and biochemistry) at 24 hours
- Brief physical examination, can be performed any time prior to discharge (Day 4)

The procedures listed above for Treatment Period 1 will be repeated for Treatment Period 2 and Treatment Period 3. Patients will be instructed to return in 7 to 21 days (taken from last dose of study medication on Day 3) for the next visit, or if Treatment Period 3, to return in 4 to 10 days (from Day 4) for the end of study visit.

6.5 End of Study Visit

The following will be performed:

- Full physical examination
- Vital signs
- Spirometry (pre-bronchodilator)
- Blood and urine samples for laboratory safety tests (haematology, biochemistry, urinalysis)
- Urine pregnancy (females of childbearing potential)
- 12-lead ECG
- Questioning for adverse events

7 STUDY METHODOLOGY

7.1 Demographics, Baseline Characteristics and Eligibility Assessments

Safety assessments (laboratory safety assessments, vital signs, 12-lead ECG and physical examination) will be performed at screening as part of the eligibility assessment as described in Section 7.4.2 to Section 7.4.5.

7.1.1 Demographic Variables

Demographic variables, including date of birth, sex, height, weight, BMI (weight $[kg]/height [m]^2$), race and smoking status will be collected at screening.

7.1.2 Medical/Surgical and Disease History

All active medical conditions and all surgeries will be recorded at screening. Disease history, including date of diagnosis and prior respiratory therapies will also be recorded.

7.1.3 Reversibility Test

Reversibility in response to salbutamol will be assessed at screening as an eligibility measure. Spirometry (FEV₁ and FVC) assessment before and after four puffs (400 mcg) of salbutamol administered using a pMDI will be performed.

Three technically acceptable measurements should be made and recorded in the eCRF. Spirometry assessments may be performed up to eight times to obtain three acceptable readings according to ATS guidelines (Miller et al, 2005). The highest reading from each assessment will be used for calculation of predicted values and increase from baseline.

The following must be confirmed for inclusion:

- Post-bronchodilator FEV_1/FVC ratio of ≤ 0.70
- Post-bronchodilator $FEV_1 \ge 40$ % and $\le 80\%$ of predicted normal*
- Demonstrates $\geq 150 \text{ mL}$ increase from pre-bronchodilator FEV₁

*NHANES III (Hankinson et al, 1999) will be used as a reference for normal predicted values.

7.1.4 Screening Laboratory Eligibility Assessments

At screening, blood samples will be taken and tested at the Local Laboratory for human immunodeficiency virus, hepatitis B and hepatitis C serology. All female patients of childbearing potential will have a serum pregnancy test.

A chest X-ray (post-anterior) must be performed at screening or in the 12 months prior to screening.

An alcohol breath test will be performed by the study centre at screening. Urine pregnancy tests for female patients of childbearing potential will also be performed by the study centre at screening (confirmed to be negative prior to the chest X-ray), on Day 1 of each treatment period and at the end of study visit.

Unscheduled and/or repeat testing may be performed at the discretion of the Investigator.

7.1.5 **Prior and Concomitant Medications and Therapies**

Prior COPD therapies and medications will be recorded at screening and concomitant use during the study recorded as described in Section 5.9.1.

Other prior medications will be separately recorded at screening and concomitant use during the study recorded as described in Section 5.9.2.

7.1.6 Eligibility Check

Patients will be confirmed as eligible according to the inclusion and exclusion criteria from assessments made at screening with a final check of all results pre-dose in Treatment Period 1.

7.2 Pharmacodynamic Assessments

7.2.1 Pulmonary Function Tests

Spirometry (FEV₁ and FVC) will be performed at screening, the end of study visit and the following time points in each treatment period:

- Day 1: pre-dose; 5, 15 and 30 minutes and 1, 1.5, 2, 4, 6, 8 and 12 hours
- Day 2: pre-dose; 15 and 30 minutes and 1, 2, 3 and 4 hours
- Day 3: pre-dose; 5, 15 and 30 minutes and 1, 1.5, 2, 4, 6, 8, 12, 15 and 24 hours

Post-dose measurements will be taken in relation to the morning dose of tiotropium DPI and RPL554 or placebo. The 12 hour measurement will therefore be taken pre-dose before the evening dose of RPL554 or placebo. The 24 hour measurement on Day 3 will be taken in the morning on Day 4 prior to discharge from the study centre.

Spirometry assessments will be made in accordance with ATS/ERS guidelines (Miller et al, 2005). At all timepoints, three technically acceptable measurements should be made and recorded. Spirometry assessments may be performed up to eight times to obtain three acceptable readings according to ATS guidelines (Miller, 2005). The highest FEV_1 and FVC readings from each assessment will be used for analysis even if the FEV_1 and FVC values come from two different forced exhalations.

7.2.2 Whole Body Plethysmography

Whole body plethysmography training and assessment for ability to perform the procedure will be conducted at screening.

Whole body plethysmography will be performed pre-dose on Day 1 and pre-dose and 1.25 hours post-dose on Day 2 of each treatment period. Assessments will be made in accordance with ATS/ERS guidelines (Wanger et al, 2005).

Patients will be placed on a body box for plethysmographic determination of lung volumes, to include RV, FRC and total lung capacity (TLC). Additionally, measurements will be made of sG_{aw} and airway resistance (R_{aw}).

7.3 Pharmacokinetic Assessments

Pharmacokinetic analysis will be performed on samples taken from patients on Day 3 of each treatment period. Blood samples (4 mL at each time point) will be collected at the following timepoints: pre-dose, 5, 30 and 45 minutes and 1, 1.5, 2, 4, 8, 12, 15 and 24 hours post-dose (the 24 hour sample will be taken in the morning on Day 4 prior to discharge from the study centre). Samples will be collected by venepuncture or via indwelling cannula in the forearm into lithium heparin tubes and will be immediately chilled (ice bath). The blood will be centrifuged within 30 minutes of collection. The plasma will be separated in a refrigerated centrifuge (about 4°C) at 1100g for 15 minutes and transferred into polypropylene tubes.

After each blood collection, the plasma will be dispensed into two aliquots. After appropriate labelling, the plasma samples will be stored at, or below -20°C. The plasma samples will then be transported in dry ice to an external laboratory where they will be stored at or below -20° C until they are submitted for analysis with a validated method. Analysis will be performed by a Central Laboratory.

7.4 Safety Assessments

7.4.1 Adverse Events

Recording and reporting adverse events is described in detail in Section 8.

7.4.2 Laboratory Safety Tests

In addition to the laboratory tests detailed in Section 7.4.2.1 to Section 7.4.2.3, unscheduled and/or repeat testing may be performed at the discretion of the Investigator. Any additional laboratory results will also be merged into the final database. Laboratory results will be provided to the Investigator for each patient and each visit. The Investigator should assign whether each abnormal result is not clinically significant or a clinically significant by manually annotating a print out of the results.

Samples will be taken and handled according to the laboratory manual and analysed at an approved Local Laboratory.

7.4.2.1 Haematology

The following will be measured at screening, on Day 4 of each treatment period and at the end of study visit: Haemoglobin, haematocrit, total white cell count, leukocyte differential count and platelet count.

At each timepoint, a sample of venous blood will be collected in a collection tube containing ethylenediaminetetraacetic acid (EDTA).

7.4.2.2 Biochemistry

The following will be measured at screening, on Day 4 of each treatment period and at the end of study visit: creatinine, total bilirubin, alkaline phosphatase, aspartate aminotransferase, alanine transaminase, gamma-GT, lactate dehydrogenase, creatine kinase, thyroid stimulating hormone, triiodothyronine and thyroxine, glucose, potassium, sodium and calcium.

At each timepoint, a sample of venous blood will be collected in a vacutainer collection tube.

7.4.2.3 Urinalysis

A midstream urine sample will be collected in a sterile container at screening and at the end of study visit. The following will be tested: leukocytes, blood, ketones, bilirubin, urobilinogen, protein and glucose.

If urinalysis on Dipstick is positive for leucocytes and/or blood/haemoglobin, a microscopic examination including erythrocytes, leucocytes, bacteria, casts, epithelial cells and crystals will be performed.

7.4.3 Vital Signs

Blood pressure and pulse rate will be measured at screening, the end of study visit and the following time points in each treatment period:

- Day 1: pre-dose; 30 minutes and 1, 2, 4, 6, 8 and 12 hours post-dose
- Day 2: pre-dose; 30 minutes and 1, 2, 3, 4 and 12 hours post-dose
- Day 3; pre-dose; 30 minutes and 1, 2, 4, 6, 8 and 24 hours post-dose

Post-dose measurements will be taken in relation to the morning dose of tiotropium DPI and RPL554 or placebo. The 12 hour measurement will therefore be taken pre-dose before the evening dose of RPL554 or placebo. The 24 hour measurement on Day 3 will be taken in the morning on Day 4 prior to discharge from the study centre.

At each timepoint, supine vital signs will be assessed whilst the patient has been at rest for at least 5 minutes.

7.4.4 Physical Examination

A full physical examination, covering major body systems (assessments of the nose, throat, skin, thyroid gland, neurological system, respiratory system, cardiovascular system, abdomen [liver and spleen], lymph nodes and extremities) will be performed at screening. Results will be recorded in the eCRF as normal, abnormal not clinically significant or abnormal clinically significant and abnormal results described. The full physical examination will be repeated at the end of study visit, and any changes only recorded.

A brief physical examination, including assessments of the skin, respiratory system, cardiovascular system, and abdomen (liver and spleen).will be performed pre-dose on Day 1 and prior to discharge from the study centre on Day 4.

7.4.5 12-Lead ECG

12-lead ECGs will be performed at screening, the end of study visit and the following time points in each treatment period:

- Day 1: pre-dose; 2 and 4 hours post-dose
- Day 2: pre-dose; 2 hours post-dose
- Day 3: pre-dose; 2, 4 and 24 hours post-dose

Post-dose measurements will be taken in relation to the morning dose of tiotropium DPI and RPL554 or placebo. The 24 hour measurement on Day 3 will be taken in the morning on Day 4 prior to discharge from the study centre.

Each 12-lead ECG should be taken after at least 5 minutes in the supine position. An overall assessment (normal, abnormal not clinically significant or abnormal clinically significant) will be recorded in the eCRF by the Investigator.

Each 12-lead ECG recording will be sent to a central vendor for interpretation.

7.4.6 Holter Monitoring

12-lead Holter monitors will be used to perform 24 hour Holter monitoring. A Holter monitor will be placed at screening, monitoring will be ambulatory and will be recorded as an outpatient and the monitor will be removed at the study centre after 24 hours. The screening Holter report must have a minimum of 18 hours recording that is evaluable for rhythm analysis and the report must be reviewed to assess inclusion criteria prior to randomisation.

A Holter monitor will also be placed at least 30 minutes pre-dose on Day 2 of each treatment period and removed after at least 24 hours post-dose and pre-dose on Day 3.

Holter readings will be sent to a central vendor for interpretation.

7.5 Appropriateness of Measurements

The assessments planned in this study are recognised as reliable, accurate and relevant.

Plasma concentrations of RPL554 will be evaluated using a validated assay and quality control samples will be analysed throughout the study. The concentrations will be used to determine within run, between run and overall precision and accuracy of the method. The procedures, including the limits of quantitation and results will be described in detail in a separate bioanalytical protocol and report. The timing of pharmacokinetic samples is deemed appropriate to establish the exposure of patients.

Spirometry is a standard lung function test used to screen for, and monitor, respiratory disease. Spirometry will be performed in accordance with ATS/ERS task force standardisation guidelines (Miller et al, 2005). Spirometers must be maintained and calibrated according to manufacturers' guidelines. Whole body plethysmography is a further non-invasive method to obtain information on airway obstruction (airway resistance) and lung volumes that is not available through spirometry. This method of assessing the functional state of the airways is of value for characterising the multiple, heterogeneous alterations occurring in patients with COPD. Whole body plethysmography will be performed in accordance with ATS/ERS task force standardisation guidelines (Wanger et al, 2005). Both spirometry and whole body plethysmography will be performed using the study centre's standard equipment and standard operating procedures (SOPs).

Physical examinations, vital signs, 12-lead ECGs, adverse event recording and laboratory safety tests are standard assessments of safety and tolerability. The range of assessments to be performed is deemed appropriate to detect any safety signals.

Holter monitoring is a standard method of continuously recording heart activity over periods of at least 24 hours. Interpretation will be performed by a specialised central vendor.

8 HANDLING OF ADVERSE EVENTS AND PREGNANCIES

8.1 Adverse Event Definitions

Adverse event is defined as any undesirable experience occurring to a patient, or worsening in a patient, during a clinical study, whether or not considered related to the study treatment. An adverse event may be any of the following:

- 1. A new illness
- 2. An exacerbation of a sign or symptom of the underlying condition under treatment or of a concomitant illness
- 3. Unrelated to participation in the clinical study or an effect of the study treatment
- 4. A combination of one or more of the above factors

No causal relationship with the study treatment is implied by the use of the term "adverse event." An exacerbation of a pre-existing condition or illness is defined as a more frequent occurrence or as an increase in the severity of the pre-existing condition or illness during the study. Planned or elective surgical or invasive procedures for pre-existing conditions that have not worsened are not adverse events. However, any complication that occurs during a planned or elective surgery is an adverse event (if the event fits the serious criteria, such as an extended hospitalisation, it will be considered to be serious). Conditions leading to unplanned surgical procedures may be adverse events.

Adverse reaction is defined as all untoward and unintended responses to study treatment related to any dose administered.

Serious adverse event (SAE) is any adverse experience that:

- Results in death
- Is life-threatening
- Requires inpatient hospitalisation or prolongation of existing hospitalisation
- Results in persistent or significant disability/incapacity, OR
- Is a congenital anomaly/birth defect
- Other medical events*

*Important medical events that may not be immediately life-threatening or result in death or hospitalisation may be considered a SAE when, based on appropriate medical judgement, they may jeopardise the patient or may require medical or surgical intervention to prevent one of the outcomes listed above.

An unexpected adverse reaction is an adverse reaction in which the nature or severity of which is not consistent with the Investigator Brochure.

Suspected unexpected serious adverse reactions (SUSAR) is any suspected adverse reaction related to the study drug that is both unexpected and serious.

8.2 **Recording and Assessing Adverse Events**

All adverse events, whether reported spontaneously by the patient, in response to open questioning on treatment days or observed by the Investigator or his/her staff, will be recorded from informed consent until the end of study visit. The start and stop time will be recorded and adverse events will be assessed by the Investigator for the following:

8.2.1 Severity

Mild:	Resolved without treatment
Moderate:	Resolved or was tolerated with specific treatment without affecting study activities
Severe:	Did not resolve or was not tolerated with treatment

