4.3.1 Study Treatment Discontinuation

Study treatment must be discontinued for the following reasons:

- Unacceptable toxicity related to study treatment
- Intolerable or persistent adverse events of any severity
- General or specific changes in the patient's condition rendering the patient unacceptable for further treatment in the judgment of the Investigator
- Clinically significant progression of disease
- Pregnancy in a female patient

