8.2.2 Chronicity

Single occasion:	Single event with limited duration
Intermittent:	Several episodes of an event, each of limited duration
Persistent:	Event which remained indefinitely

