8.2.4 Action and Outcome

- Action taken with study treatment (none, study treatment stopped, study treatment temporarily interrupted)
- Other actions (none, concomitant medication, study discontinuation, hospitalisation, other)
- The outcome and date of outcome according to the following definitions:
 - Recovered or resolved (adverse event disappeared)
 - Recovering or resolving (patient is recovering)
 - Not recovered or not resolved (adverse event remains without signs of improvement)
 - Recovered or resolved with sequelae (adverse event has resulted in permanent disability or incapacity)
 - Fatal
 - Unknown (only applicable if patient has been lost to follow-up)
- Seriousness (yes or no)

8.3 **Reporting Procedure for SAEs**

The Investigator must report all SAEs to the Sponsor in writing using the Sponsor's reporting form and emailed (email address included on Page 2) to as soon as practical, but in no case should it be more than 24 hours of awareness. Any SAEs notified in the 30 day period after the last dose of study treatment must also be reported

SUSARs will be determined by the Sponsor's Medical Monitor.

SAEs will be reported to the ethics committee(s) and regulatory authority(ies) according to local requirements.

All adverse events will be followed until they have abated, or until a stable situation has been reached. Depending on the event, follow up may require additional tests or medical procedures as indicated, and/or referral to the patient's general physician or a medical specialist.

It is the responsibility of the Investigator to ensure that any necessary additional therapeutic measures and follow-up procedures are performed.

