10.4.7 Safety

Safety data including safety laboratory tests, 12-lead ECG and Holter parameters, vital signs and physical examinations, will be summarised by treatment group and time point of collection, when appropriate. For continuous variables, the change from baseline (pre-dose at each treatment visit) to each post-dose time point will also be calculated and summarised. Data will further be illustrated by shift tables (showing changes from low/normal/high) and shift plots for selected time points. Separate listings will be generated of abnormal values occurring after the first dose of study treatment.

Coded adverse event terms will be presented by system organ class (SOC) and preferred term and summarised by treatment group. A summary table by treatment group with total number and number of patients with adverse events, SAEs, adverse events leading to discontinuation of study treatment, causally related adverse events and severe adverse events will be produced. Further SAEs, causally related adverse events and adverse event of each intensity will be summarised by SOC and preferred term.

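### Protocol 8.2.1 grades adverse event severity by resolution, treatment and tolerance instead of intensity, and the grades overlap and leave gaps

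*Protocol*

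**What the plan says.** Protocol 8.2.1 is the only definition of severity in either document. It has three grades:

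- The lowest grade, mild, reads "Resolved without treatment".
- The middle grade, moderate, reads "Resolved or was tolerated with specific treatment without affecting study activities".
- The highest grade, severe, reads "Did not resolve or was not tolerated with treatment".

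Neighbouring sections record the same features separately. Chronicity (8.2.2) has a persistent category, "Event which remained indefinitely". Action and outcome (8.2.4) has a field for concomitant medication given for the event and an outcome category that begins "Not recovered or not resolved (adverse event remains without signs of improvement". Seriousness is a further yes/no item in 8.2.4.

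For the analysis, Protocol 10.4.7 has an overview row for severe events and adds that "adverse event of each intensity will be summarised by SOC and preferred term". SAP 6.18.1 tabulates treatment-emergent events as mild, moderate or severe, overall and by system organ class and preferred term, and counts each patient at the worst severity. The SAP offers no definition of its own, and its list of changes from the protocol (6.19) does not mention severity.

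**The concern.** A severity grade should say how bad an event was while it lasted. This one says mainly how the event ended and whether it was treated, which other fields already hold. The one functional element, the effect on study activities, appears only in the moderate grade. The tables promised in 10.4.7 as summaries by intensity would therefore not show intensity.

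Tolerability and safety is a secondary objective, and the trial compares two doses with placebo. Protocol 1.2 reports a transient increase in dizziness in COPD patients on multiple doses. A short, untreated episode of dizziness is mild under 8.2.1 whatever its force. If such events were more intense at 6 mg than at 1.5 mg or placebo, the severity tables could not show it. In the other direction, a minor symptom that never quite clears may enter the severe row.

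Overlaps and gaps add a second problem: two investigators could grade the same event differently and both be following the protocol.

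**Working it through.** No arithmetic applies and the plan states no figure to reproduce. The check is to run every combination of resolved, treated and tolerated through the three definitions. In the moderate grade, both closing qualifiers (with treatment, and no effect on study activities) are taken to apply to both verbs.

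| Case | Resolved | Treated | Tolerated with treatment | Grade under 8.2.1 |
|---|---|---|---|---|
| 1 | Yes | No | n/a | Mild, at any intensity |
| 2 | Yes | Yes | Yes | Moderate if study activities were unaffected; otherwise none |
| 3 | Yes | Yes | No | Severe; also moderate if study activities were unaffected |
| 4 | No | Yes | Yes | Severe; also moderate if study activities were unaffected |
| 5 | No | Yes | No | Severe |
| 6 | No | No | n/a | Severe on the literal reading; none if the treatment phrase governs both verbs |

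How far each result depends on the reading:

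- **Case 1** is mild on any reading. Intensity plays no part.
- **Case 4** overlaps on any reading. The event was tolerated with treatment and study activities were unaffected, so it is moderate. It did not resolve, with treatment or otherwise, so it is also severe.
- **Case 2** has a gap if the clause on study activities applies to resolved events as well as tolerated ones, which is the natural reading. If both qualifiers attach only to the second verb, the gap closes, but every untreated event that resolved is then both mild and moderate.
- **Case 6** depends on the scope of the treatment phrase in the severe grade. Either result is a defect: a minor event is called severe, or it has no grade.

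Two other places in the protocol do not fit the rule. Section 4.3.1 lists "Intolerable or persistent adverse events of any severity" among the reasons to discontinue treatment, which treats persistence and severity as independent. Under 8.2.1 they are not, because non-resolution is itself a criterion for severe. Section 10.4.7 uses intensity as the name of the tabulated scale, and no section collects intensity.

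The grade reaches the results through the overview row and the tables in Protocol 10.4.7, and through the tables in SAP 6.18.1. Because the SAP takes the worst grade per patient, one event placed in severe sets that patient's category for that preferred term and organ class.

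**The case against.** The best case for leaving the text alone is that little depends on it. Seriousness, outcome, chronicity, treatment and start and stop times are all recorded, so the listings let a reader see why an event was graded as it was. The same scale applies to all three treatments under a blinded investigator. Discontinuation under 4.3.1 does not depend on severity. Cardiovascular effects have their own numerical summaries in SAP 6.18.3 to 6.18.5 and 6.18.7. Protocol 10.4.7 may simply use intensity as a synonym for severity. All of this stands, and it limits the consequence. It does not supply the missing intensity criterion or make the grades exclusive.

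Several stronger readings are tempting, but the documents do not support them:

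- **That every event still ongoing at the end is severe.** A treated, tolerated one also fits moderate (case 4), and an untreated one may have no grade (case 6). Protocol 8.3 also follows events until they abate or become stable. The clearest exposure is therefore to untreated minor events that stabilise without resolving.
- **That the severe row would be inflated by a known amount.** Two such events give 2/30 = 6.7% to 2/24 = 8.3% only if they occur in two different patients under the same treatment. Both in one patient, for the same preferred term under one treatment, give 1/30 = 3.3% to 1/24 = 4.2%. The count of two is an assumption, and the documents give no rate of ongoing events.
- **That intense palpitations or dizziness are expected here.** Protocol 1.2 calls the common events generally mild and links dose-related palpitations to 24 mg. This trial gives 1.5 mg and 6 mg.
- **That safety reporting is compromised.** Serious events are identified by the criteria in 8.1, not by the 8.2.1 grade. Section 8.1 does mention severity when defining an unexpected reaction, but nothing ties that judgement to the 8.2.1 grade; 8.3 leaves the determination of unexpected serious reactions to the sponsor's medical monitor.

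**Conclusion.** The point holds. Protocol 8.2.1 does not measure intensity, largely repeats information held in 8.2.2 and 8.2.4, and has grades that are neither mutually exclusive nor exhaustive. Two results hold on any reading: an untreated event that resolves is mild however intense, and an unresolved event tolerated with treatment, with study activities unaffected, is both moderate and severe. The gap in case 2 and the grade in case 6 depend on how the qualifiers are read, but no reading repairs the scale.

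The size is modest and cannot be put as a number from the documents. The effect is confined to the descriptive severity summaries. No efficacy result, sample size figure or identification of a serious event depends on it. It is still worth correcting, because those summaries serve a stated secondary objective and the change is small.

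**What to change.** Replace the three lines of 8.2.1 with grades that are mutually exclusive and exhaustive and rest on intensity or interference with usual activities. For example: mild, noticed but no interference; moderate, some interference; severe, prevents usual activities. Leave resolution and treatment to 8.2.4 and persistence to 8.2.2. Use one word, severity or intensity, throughout Protocol 10.4.7 and SAP 6.18.1, and have the SAP refer to the revised definition.

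The cost is protocol text and eCRF completion guidance; no new field, visit or assessment is needed. The real downside is that events already graded would have to be regraded, and since no other field holds intensity this would have to be done from source notes. If regrading is not possible, the tables should state the definition used in a footnote and should not be labelled as summaries by intensity.
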